#### **4.2.4 Visit 7 (Week 26)**

At Visit 7 at Week 26, the following procedures will be performed:

- Recording of AEs
- Recording of concomitant medications
- IMT
- Dispense investigational product
- Investigational product compliance
- TLC counselling

#### **4.2.5 Visit 8 (Week 39)**

Subjects will be required to fast for 8 hours (water permitted) prior to Visit 8 (Week 39). Those subjects who have failed to fast for 8 hours should return for their blood draw following an 8-hour fasting period. At the visit, the following procedures will be performed:

- Recording of vital signs
- Recording of AEs
- Recording of concomitant medications
- Chemistry panel including liver function tests (ALT, AST, bilirubin, ALP), serum creatinine, and CK only
- Serum lipid profile
- Dispense investigational product
- Investigational product compliance
- TLC counselling

#### **4.2.6 Visit 9 (Week 52)**

At Visit 9 at Week 52, the following procedures will be performed:

- Recording of AEs
- Recording of concomitant medications
- IMT

- Dispense investigational product
- Investigational product compliance
- TLC counselling

#### **4.2.7 Visit 10 (Week 65)**

Subjects will be required to fast for 8 hours (water permitted) prior to Visit 10 (Week 65). Those subjects who have failed to fast for 8 hours should return for their blood draw following an 8-hour fasting period. At the visit, the following procedures will be performed:

- Recording of vital signs
- Recording of AEs
- Recording of concomitant medications
- Chemistry panel including liver function tests (ALT, AST, bilirubin, ALP), serum creatinine, and CK only
- Serum lipid profile
- Dispense investigational product
- Investigational product compliance
- TLC counselling

#### **4.2.8 Visit 11 (Week 78)**

At Visit 11 at Week 78, the following procedures will be performed:

- Recording of AEs
- Recording of concomitant medications
- IMT
- Dispense investigational product
- Investigational product compliance
- TLC counselling

#### **4.2.9 Visit 12 (Week 91)**

Subjects will be required to fast for 8 hours (water permitted) prior to Visit 12 (Week 91). Those subjects who have failed to fast for 8 hours should return for their blood draw following an 8-hour fasting period. At the visit, the following procedures will be performed:

- Recording of vital signs
- Recording of AEs
- Recording of concomitant medications
- Chemistry panel including liver function tests (ALT, AST, bilirubin, ALP), serum creatinine, and CK only
- Serum lipid profile
- Dispense investigational product
- Investigational product compliance
- TLC counselling

#### **4.2.10 Visit 13 (Week 104)**

Subjects will be required to fast for 8 hours (water permitted) prior to Visit 13 (Week 104). Those subjects who have failed to fast for 8 hours should return for their blood draw following an 8-hour fasting period. If, at the final visit, the subject has failed to fast, the subject should remain on investigational product until the blood samples have been drawn.

At this last visit during the treatment period (Visit 13), the following procedures will be performed:

- Recording of vital signs
- Measurement of body weight
- Recording of AEs
- Recording of concomitant medications
- Physical examination
- ECG
- Chemistry panel
- Hematology

- Urine sample for complete urinalysis
- Serum lipid profile
- ApoA-I and ApoB
- IMT (2 IMT procedures for Visit 13 are to be performed on different days when possible with the second IMT procedure occurring on or before Visit 13)
- Investigational product compliance

The final 2 IMT procedures will be scheduled before discontinuation of study treatment. The second of the final 2 IMT procedures will occur at or before Visit 13 (Week 104), at the time of discontinuation of the study treatment.

#### **4.2.11 Early Termination Visit**

The term "early termination" refers to a subject's non-completion of a study whether by his or her own choice or the investigator's decision or due to discontinuation of the study by the Sponsor.

In the absence of a medical contraindication or significant protocol violation, every effort will be made by the principal investigator to keep the subject in the study. Should the subject decide to withdraw, an attempt will be made to conduct an Early Termination (ET) Visit within 1 week of discontinuation of study treatment. The ET visit will include all procedures normally done at Visit 13 (Week 104) except the IMT procedures. A single IMT is to be performed on any subject who withdraws after 26 weeks.

The primary reason for a subject withdrawing prematurely should be recorded on the eCRF.

The investigator should notify the Study Physician promptly when a subject is withdrawn, or if the study is stopped at their site by the Independent Ethics Committee/Institutional Review Board, or if the investigator elects to stop the study.

### **4.3 Follow-up period**

A follow-up period is not planned for this study.

## **5. STUDY ASSESSMENTS**

The Rave Web Based Data Capture (WBDC) system will be used for data collection and query handling. The investigator will ensure that data are recorded on the eCRF as specified in the study protocol and in accordance with the instructions provided.

The investigator ensures the accuracy, completeness, and timeliness of the data recorded and of the provision of answers to data queries according to the Clinical Study Agreement. The

investigator will sign the completed eCRFs. A copy of the completed eCRFs will be archived at the study site.

## 5.1 Efficacy assessments

### 5.1.1 IMT Assessment

IMT assessment will be conducted at the times indicated in the Study Plan shown in [Table 1](#). The images will be centrally evaluated at **CCI** or **CCI**.

Intima-media thickness measurements will be made from ultrasound images of the carotid arteries. The thickness of the intima and media is determined as the distance from the interface between the vessel lumen and the intima, to the interface between the media and the adventitia. At each imaging visit, subjects will lie in a supine position with their head turned to the opposite side away from the artery that is being examined. Images will be made of the near and far walls of the CCA, the carotid bulb, and the ICA segments of the right and left carotid arteries. The standard protocol requires each of these 12 artery segments to be imaged from 3 interrogation angles, each of which differs from the adjacent orientation by 30° of angulation (see Appendix G). The images will be recorded and sent to **CCI** for evaluation.

For each carotid artery segment, the images recorded at the various interrogation angles will be measured to determine the largest IMT in each image. The maximum IMT measured from the individual interrogation angles will be entered as the IMT value for that arterial segment. This process is repeated for the 12 carotid arterial segments: the near and far walls of the CCA, the carotid bulb, and the ICA segments of the right and left carotid arteries.

### 5.1.2 Lipid parameters

Blood samples for analysis of lipid parameters will be collected at the times indicated in the Study Plan shown in [Table 1](#).

Subjects must fast for at least 8 hours and must have been sitting for at least 5 minutes before blood samples are taken for lipid assays. If a subject attends a study visit without having fasted for 8 hours, he or she must be asked to return at another time within the visit window for the study visit.

The central laboratory will provide the investigational sites with all the appropriate materials for specimen collection and sample processing, packaging, and shipping to the central laboratory. A central laboratory manual providing detailed instructions will be provided to each investigational site before trial start.

The principal investigator will ensure that samples are labelled and shipped in accordance with the Laboratory Manual and the Biological Substance, Category B Regulations (materials containing or suspected to contain infectious substances that do not meet Category A criteria), see Appendix B. Any samples identified as Infectious Category A materials are not to be

shipped, and no further samples will be taken from the subject unless agreed with AstraZeneca and appropriate labelling, shipment and containment provisions are approved.

Sample analysis will be carried out in the central laboratory.

## **5.2 Safety assessments**

Safety will be assessed by the incidence of AEs, SAEs, AEs leading to discontinuation, changes in clinical laboratory analyses (chemistry, hematology, and urinalysis), vital signs, 12-lead ECGs, and physical examination during treatment with rosuvastatin. The collection of AEs is described in Section 6 and the other safety assessments are detailed below.

### **5.2.1 Laboratory safety assessments**

Blood and urine samples for determination of clinical chemistry, hematology, and urinalysis will be taken at the times indicated in the Study Plan in Table 1. A full clinical chemistry will be performed at Visit 1 (Week -6), Visit 4 (Week 0), Visit 5 (Week 6), Visit 6 (Week 13), and Visit 13 (Week 104), and an abbreviated chemistry panel including liver function tests (ALT, AST, bilirubin and ALP), serum creatinine, and CK only will be performed at Visit 8 (Week 39), Visit 10 (Week 65), and Visit 12 (Week 91). Additional safety samples may be collected if clinically indicated at the discretion of the investigator. The date and time of collection will be recorded on the appropriate eCRF.

All safety laboratory analyses, other than urine pregnancy tests, will be performed by a central laboratory. The safety laboratory samples will be disposed of after analysis. The central laboratory will provide all collection materials and instructions for sample collection, packaging, and shipment. Urine pregnancy tests will be performed at the clinical sites.

The laboratory variables shown in Table 2 will be measured.

**Table 2 Laboratory Safety Assessments**

Hematology (whole blood)	Clinical Chemistry (serum or plasma)	Urinalysis
Hemoglobin	Alanine aminotransferase	Color
Erythrocytes	Aspartate aminotransferase	Appearance
Hematocrit	Creatine kinase	Specific gravity
Leukocyte cell count	Gamma-glutamyltransferase	Urine reaction pH
Platelet count	Alkaline phosphatase	Glucose
Red cell distribution width	Total bilirubin	Protein (qualitative)
Mean corpuscular volume	Sodium	Ketones
Mean corpuscular hemoglobin	Potassium	Bilirubin
Mean corpuscular hemoglobin concentration	Calcium	Occult blood
Percentage differential leukocyte count	Total protein	Microscopic analysis of any formed elements
	Phosphate	
	Albumin	
	Creatinine	
	Fasting blood glucose	

The investigator should make an assessment of the available results with regard to clinically relevant abnormalities. The laboratory results should be signed and dated and retained at the center as source data for laboratory variables. For information on how AEs based on laboratory tests should be recorded and reported, see Section 6.3.

Note: If CK is  $\geq 5$  x ULN, see Appendix D.

Note: If a subject has ALT or AST  $>3$  x ULN, it is recommended to discontinue the investigational product. See Appendix C for further instruction on cases of increases in liver biochemistry values and evaluation of Hy's Law.

### 5.2.2 Medical history and physical examination (including height and weight)

A detailed medical history, including family history of hyperlipidemia, alcohol intake, use of other medications or drugs, as well as CHD, and risk factors such as smoking, diabetes mellitus, and a family history of premature CHD will be recorded on the eCRF at Visit 1 (Week -6).

A full physical examination (including stigmata of hyperlipidemia) including cardiovascular system, respiratory system, central nervous system, skin, gastrointestinal system, musculoskeletal system, endocrine system, ears, nose and throat, eyes, and lymph nodes will be recorded at the times indicated in the Study Plan in Table 1. Weight will be recorded at Visit 1 (Week -6), Visit 4 (Week 0), and Visit 13 (Week 104), and height will be recorded only at Visit 1 (Week -6).

### **5.2.3 ECG**

A 12-lead ECG will be performed after the subject has been lying down for 5 minutes at the times indicated in the Study Plan in [Table 1](#). Heart rate, P and QRS durations, PR, QT and QTc intervals will be recorded from standard lead of the computerized quantitative 12-lead ECG.

For information on how AEs based on ECGs should be recorded and reported, see [Section 6.3](#).

### **5.2.4 Vital signs**

Blood pressure and resting heart rate will be measured at the times indicated in the Study Plan in [Table 1](#). Blood pressure will be measured after the subject has been resting for 5 minutes, using a standard non-invasive equipment and recorded. Heart rate will be taken manually from the radial pulse.

For information on how AEs based on vital signs should be recorded and reported, see [Section 6.3](#).

## **5.3 Other assessments**

### **5.3.1 Risk assessment**

During the screening period at Visit 1 (Week -6), subjects will be evaluated using the risk assessment introduced in the 2007 China Adult Dyslipidemia Management Guidelines (see [Appendix F](#)). Patients with existing CHD (or a CHD risk equivalent) are at the highest risk and will be excluded from participation. According to the guideline, hypertension plays a role equal to that of any 3 other risk factors. Thus, subjects with hypertension and 3 or more additional CVD risk factors will be regarded as at high risk and will be excluded from participation. The risk assessment will be determined according to the counting of categorical CVD risk factors of age, hypertension, smoking, obesity, family history of premature CHD, and HDL-C (see [Appendix F](#)).

### **5.4 Pharmacokinetics**

Pharmacokinetic samples will not be taken during the study.

### **5.5 Pharmacodynamics**

Pharmacodynamic samples will not be taken during the study.

### **5.6 Pharmacogenetics**

Pharmacogenetic samples will not be taken during the study.

### **5.7 Biomarker analysis**

Biomarkers will not be assessed in this study.

## **6. SAFETY REPORTING AND MEDICAL MANAGEMENT**

The principal investigator is responsible for ensuring that all staff involved in the study are familiar with the content of this section.

### **6.1 Definition of adverse events**

An AE is the development of an undesirable medical condition or the deterioration of a pre-existing medical condition following or during exposure to a pharmaceutical product, whether or not considered causally related to the product. An undesirable medical condition can be symptoms (eg, nausea, chest pain), signs (eg, tachycardia, enlarged liver) or the abnormal results of an investigation (eg, laboratory findings, electrocardiogram). In clinical studies, an AE can include an undesirable medical condition occurring at any time, including run-in or washout periods, even if no study treatment has been administered.

The term AE is used to include both serious and non-serious AEs.

### **6.2 Definitions of serious adverse event**

A serious adverse event is an AE occurring during any study phase (ie, screening, treatment, follow-up), that fulfills one or more of the following criteria:

- Results in death
- Is immediately life-threatening
- Requires in-patient hospitalization or prolongation of existing hospitalization
- Results in persistent or significant disability/incapacity or substantial disruption of the ability to conduct normal life functions
- Is a congenital abnormality or birth defect
- Is an important medical event that may jeopardize the subject or may require medical intervention to prevent one of the outcomes listed above

For further guidance on the definition of an SAE, see Appendix A.

### **6.3 Recording of adverse events**

#### **6.3.1 Time period for collection of adverse events**

All AEs, including SAEs, will be collected from the time of signature of the informed consent throughout the treatment period and within 10 days after last dose of study drug.

#### **6.3.2 Follow-up of unresolved adverse events**

Any AEs that are unresolved at subject's last visit/ contact in the study are followed up by the investigator for as long as medically indicated, but without further recording in the eCRF.

AstraZeneca retains the right to request additional information for any subject with ongoing AE(s)/SAE(s) at the end of the study, if judged necessary.

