## 6.4 Reporting of serious adverse events

All SAEs have to be reported, whether or not considered causally related to the investigational product, or to the study procedure(s). All SAEs will be recorded in the eCRF.

If any SAE occurs in the course of the study, then investigators or other site personnel inform the appropriate AstraZeneca representatives within 1 day (ie, immediately but **no later than 24 hours**) of when he or she becomes aware of it.

The designated AstraZeneca representative works with the investigator to ensure that all the necessary information is provided to the AstraZeneca Patient Safety data entry site **within 1 calendar day** of initial receipt for fatal and life-threatening events **and within 5 calendar days** of initial receipt for all other SAEs.

For fatal or life-threatening AEs where important or relevant information is missing, active follow-up is undertaken immediately. Investigators or other site personnel inform AstraZeneca representatives of any follow-up information on a previously reported SAE within 1 calendar day (ie, immediately but **no later than 24 hours**) of when he or she becomes aware of it.

Once the investigators or other site personnel indicate an AE is serious in the WBDC system, an automated email alert is sent to the designated AstraZeneca representative.

If the WBDC system is not available, then the investigator or other study site personnel reports an SAE to the appropriate AstraZeneca representative by telephone.

The AstraZeneca representative will advise the investigator/study site personnel how to proceed.

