4.4.2 All adverse events

The subject incidence of AEs reported during the screening phase will be summarised by all AEs, Deaths, SAEs, and withdrawal from study due to AE.

The subject incidence of treatment emergent AEs will be summarized by treatment group in the following ways:

- All AEs, (by severity)
- AEs classified as related to study drug
- Deaths
- SAEs (by severity, and excluding where the outcome was death)
- AEs leading to study discontinuation

The subject incidence of treatment emergent AEs will be summarized separately by SOC, PT and treatment group for the double-blind treatment period.

The subject incidence of the most common (reported in at least 2% of the subjects in any treatment group) treatment emergent AEs will be presented by SOC, PT and treatment group. Also, the subject incidence of treatment emergent AEs will be presented by PT, intensity and treatment group. The subject incidence of ischaemic cardiovascular AEs will also be presented by PT. Ischaemic cardiovascular AEs will be identified using key words of ‘myocardial infarction’, ‘acute coronary syndrome’, ‘unstable angina’(or angina unstable), ‘stroke’ (excluding heat stroke), ‘cerebrovascular accident’, ‘cerebral infarction’. A subject listing of all reported AEs during the screening and the double-blind treatment period will be produced.

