4.4.3 Deaths

All deaths recorded on the TERM page, the AE page, or SAE page (with a death date, cause of death, outcome or SAE categorization present) of the CRF will be considered a death in the analyses. All deaths will be summarized by SOC and PT for the safety analysis. A listing of all deaths during screening and double-blind treatment period will be produced.

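### Protocol 6.3.2 ends eCRF recording at last visit or contact for unresolved SAEs as well as AEs, so a later fatal or worsened outcome may be missing from the CRF-based death, non-fatal SAE and severity summaries

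*Protocol*

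**What the plan says.** **Recording stop.** Protocol 6.3.2 covers "Any AEs that are unresolved at subject's last visit/ contact in the study". Such events "are followed up by the investigator for as long as medically indicated, but without further recording in the eCRF". Its second paragraph lets the sponsor ask for more information on ongoing AEs or SAEs if it judges this necessary, but does not say where that information is stored.

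**Scope.** Protocol 6.1: "The term AE is used to include both serious and non-serious AEs".

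**Collection window.** Protocol 6.3.1 collects AEs and SAEs from consent "throughout the treatment period and within 10 days after last dose of study drug". Protocol 4.3 plans no follow-up period.

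**SAE reporting.** Protocol 6.4 requires every SAE to be entered in the eCRF. Sites must also "inform AstraZeneca representatives of any follow-up information on a previously reported SAE within 1 calendar day", with no end date.

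**Reconciliation.** Protocol 9.4 provides for SAE reconciliation with the Patient Safety database, the site, or both.

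**Analysis.** SAP 4.6.4 summarizes AEs and SAEs by onset date, up to 10 days after the last dose. SAP 4.4.3 defines deaths by CRF source: "All deaths recorded on the TERM page, the AE page, or SAE page". SAP 4.4.2 includes a summary of "SAEs (by severity, and excluding where the outcome was death".

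**The concern.** The eCRF is the only source that the SAP names for deaths. If the eCRF closes to an SAE while it is still open, what is tabulated is its status at last contact, even when the sponsor later learns the true outcome through the safety-reporting route. The events exposed are the gravest in the trial: serious, begun on treatment or shortly after, and not resolved when the subject was last seen or contacted.

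Safety and tolerability against placebo is a stated objective, and the population is low risk, so few deaths are likely. One death shown as a non-fatal SAE could visibly alter a sparse between-arm comparison.

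**Working it through.** No arithmetic applies. The documents state no SAE or death rate, and there is no planned figure to reproduce. The check sets the sections side by side and follows one case through to the outputs.

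1. **Does the stop cover SAEs?** Yes, as written. Section 6.3.2 applies to any AE, and 6.1 defines AE to include serious events. The second paragraph of 6.3.2 names SAEs, so they were in view, but no exception was made.

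2. **When does it take effect?** At last visit or contact, not at Visit 13 as such. Visit 13 coincides with the end of treatment. For early stoppers, "an attempt will be made to conduct an Early Termination (ET) Visit within 1 week of discontinuation of study treatment". With no follow-up period, the 10-day window in 6.3.1 can run past the last visit. A later contact moves the cut-off; without one, the last visit is the cut-off.

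3. **Can later information reach the sponsor?** Yes. Under 6.4 it must, within a day, with no time limit.

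4. **Does it then reach the eCRF?** The documents do not settle this. Section 6.4 says SAEs belong in the eCRF, 6.3.2 says no further recording, and neither cites the other. Section 9.4 calls for reconciliation but does not say that a mismatch permits an entry that 6.3.2 bars. Appendix C has liver CRF modules completed as information arrives, but only for potential Hy's Law cases.

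5. **What happens to the outputs?** Take a subject with an SAE that began on treatment and is open at last contact. The subject then dies, and the site tells the sponsor within a day. The event qualifies for analysis by onset. If 6.3.2 is applied literally:

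| Output | What it depends on | Effect |
|---|---|---|
| Deaths (SAP 4.4.3) | A death-related entry on a CRF page | Death may be missing |
| SAEs excluding fatal outcome (SAP 4.4.2) | Recorded outcome | Event stays in as non-fatal |
| SAEs by severity (SAP 4.4.2) | Recorded intensity | Later worsening not shown |
| SAE incidence by SOC and PT (SAP 4.4.4) | Onset and recorded seriousness | Unchanged if already recorded as serious; an AE that becomes serious after last contact may be missing |
| CIMT and lipid analyses | Not dependent on AE records | Unchanged |

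The fields left at their last-contact value are those listed in Protocol 6.3.3, including seriousness, maximum intensity, outcome, and date and cause of death.

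**The case against.** The strongest reply is that the protocol already carries late SAE information. Section 6.4 is the SAE-specific section and can be read as governing SAEs. Section 9.4 reconciles them and also provides for data queries. Section 6.3.2 itself reserves a right to ask for more. A sponsor following all of this might well correct the eCRF. The Data Management Plan, which governs data handling, is not among the documents. Safety is summarized descriptively, without formal tests, and ending routine AE recording at last contact is a legitimate choice. All of that stands, and it limits the point to an unreconciled rule.

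Four stronger readings are tempting but not supported:

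- *A later death can never reach the tables, and the two databases are bound to diverge.* Reconciliation exists and could prompt a correction. The text only fails to say that it does.
- *Sections 6.3.1 and 6.3.2 contradict each other outright.* The example would be an AE open at Visit 13 that turns serious on day 5. If the site hears this from the subject, that is a later contact and the stop has not yet applied. The conflict arises only if there is no later contact.
- *A subject taken off drug for a stroke or MI has the outcome frozen at the Early Termination visit.* Discontinuation under Protocol 3.9 is discretionary in that case, only an attempt at the visit is required, and nothing makes it the last contact.
- *A number of lost deaths can be estimated.* That needs an SAE rate, the share open at last contact, and the share of those that later prove fatal and go unrecorded. None is in the documents.

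What the reply does not answer is that no passage says 6.4 or 9.4 overrides 6.3.2, and the SAP offers no other source for deaths.

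**Conclusion.** The concern holds as a conflict between sections that can misclassify serious outcomes. It does not show that any outcome will be lost. Section 6.3.2 is an explicit rule without an SAE exception, it is not reconciled with 6.4, and SAP 4.4.3 relies on CRF pages alone.

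The exposure is confined to deaths, the non-fatal SAE summary, severity, and AEs that become serious late. It requires that the site applies 6.3.2 literally, that the event is open at last contact, that its outcome changes or it becomes serious afterwards, and that reconciliation does not lead to an eCRF correction. How often this would happen cannot be stated from the documents. The change is worth making because it concerns the gravest events and costs little.

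**What to change.** - **Protocol 6.3.2:** limit the stop on further eCRF recording to non-serious AEs, and refer to 6.4 for SAEs.
- **SAEs:** for SAEs with onset within 10 days of the last dose, including AEs that become serious in that window, allow updates to outcome, seriousness, intensity, and date and cause of death until database lock.
- **SAP 4.4.3:** state that deaths found through the existing 9.4 reconciliation for such events are counted. Use the same source for the non-fatal SAE summary in 4.4.2, so that one subject cannot appear as a death in one table and as a non-fatal SAE in another.

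**Cost.** A wording change in each document, and a few eCRF records left open until lock. There is no extra visit and no change to clinical management, since 6.3.2 and 6.4 already require the follow-up and its reporting. One limitation remains: the time available for updates runs from each subject's last contact to lock, so it will be longer for those who leave the study early.
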